4.5 Informed Consent Process

The process for obtaining informed consent must comply with the ethical principles defined in the current version of the Declaration of Helsinki (**Appendix C**).

Prior to enrollment in the clinical study, all subjects will be consented, as required by applicable regulations and the site's Institutional Review Board (IRB) or ethics committee (EC). The consent form must be signed and dated by the subject and by the person obtaining the consent, where applicable.

The principal investigator (PI) or his/her authorized designee will conduct the informed consent process. This process will include a verbal discussion with the subject on all aspects of the clinical study that are relevant to the subject's decision to participate, and the subject should be allowed adequate time to review and ask questions.

Documentation that informed consent was obtained will be recorded on the eCRF and in the subject's medical record. The signature date on the consent form should be referenced. The original signed informed consent should be filed in the subject's study chart and a copy of the signed consent form given to the subject per IRB/EC requirements.

A template of the informed consent form is provided in **Appendix E: Sample Informed Consent**. Any changes to the informed consent must be approved by Abbott prior to ethics committee review and approval.

A subject cannot be consented for the study prior to IRB/EC approval of the informed consent form. The subject shall be provided the informed consent form that is written in a language understandable to the subject and has been approved by the site's IRB/EC.

The subject is enrolled in the study when consent has been obtained and vascular access initiated, (prospective), or when consent is obtained after a subject underwent a study device implant attempt that may have been successful or unsuccessful (retrospective). Failure to obtain informed consent from a subject must be reported to the Sponsor within 5 working days and to the reviewing center's IRB/EC according to the IRB/EC's reporting requirements.

5. Device

[figure not shown]
[figure not shown]

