6.3 Attempt to treat

Subjects who are consented, in whom vascular access for the AMPLATZER LAA Occluder was initiated, but the device was not implanted, will be considered “Attempt to Treat”. The subject will be followed for 7 days or until discharge, whichever is later. Retrospectively enrolled subjects will include “Attempt to Treat” subjects; AEs that occurred within 7 days following the implant attempt or by discharge, whichever was later, will be captured.

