14.1 Primary Endpoints

There are three primary endpoints, two effectiveness endpoints and one safety endpoint.

14.1.1 Primary Effectiveness Endpoint 1:

Primary effectiveness endpoint 1 is the occurrence of the composite of stroke (including ischemic or hemorrhagic), systemic embolism, or cardiovascular or unexplained death at 24 months.

Hypothesis:

Ho: $\lambda_1 \geq 9.6\%$

Ha: $\lambda_1 < 9.6\%$,
where λ_1 is the rate of primary composite endpoint 1 at 24 months.

Analysis Methods:

Kaplan-Meier analysis will be used to estimate the event rate of at 24 months (731 days post implant). The 97.5% upper confidence bound for the event rate must be less than 9.6% in order to declare success. [REDACTED]

Analysis Population:

Subjects in this study who receive an implant of the AMPLATZER LAA Occluder will be included in the analysis.

14.1.2 Primary Effectiveness Endpoint 2:

Primary effectiveness endpoint 2 is the occurrence of the composite of ischemic stroke or systemic embolism at 24 months.

Hypothesis:

Ho: $\lambda_2 \geq 6.6\%$

Ha: $\lambda_2 < 6.6\%$,

where λ_2 is the rate of primary composite endpoint 2 at 24 months.

Analysis Methods:

Kaplan-Meier analysis will be used to estimate the rate of event at 24 months (731 days post implant). The 97.5% upper confidence bound for the event rate must be less than 6.6% in order to declare success. [REDACTED]

Analysis Population:

Subjects in this study who receive an implant of the AMPLATZER LAA Occluder will be included in the analysis.

14.1.3 Primary Safety Endpoint:

The primary safety endpoint is the occurrence of one of the following events between the time of implant and within 7 days of the procedure or by hospital discharge, whichever is later: All-cause death, ischemic stroke, systemic embolism, or device or procedure related events requiring open cardiac surgery or major endovascular repair (percutaneous catheter drainage of pericardial effusion, snaring of an embolized device, thrombin injection to treat femoral pseudoaneurysm, and nonsurgical treatments of access site complication will not be included in the assessment of the third primary endpoint).

Hypothesis:

Ho: $P \geq 2.66\%$

Ha: $P < 2.66\%$,

where P is the proportion of subjects experiencing a primary safety event within 7 days of the procedure or by hospital discharge, whichever is later.

Analysis Methods:

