The proportion of subjects experiencing a primary safety endpoint will be estimated. The 97.5% upper confidence bound for the proportion of subjects experiencing a safety event will be calculated using the exact binomial method. The 97.5% upper confidence bound for the [REDACTED]

proportion must be less than 2.66% in order to declare success. [REDACTED]

Analysis Population:

Subjects who undergo an implant attempt with the AMPLATZER LAA Occluder will be included. An attempt is defined as a subject in whom vascular access has been initiated.

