Kaplan-Meier analysis will be used to estimate the rate of death. Subjects who are attempted to be implanted with the AMPLATZER LAA Occluder, or have been retrospectively enrolled will be included in this analysis.

Major Bleeding:

Kaplan-Meier analysis will be used to estimate the rate of major bleeding events. Major bleeding is defined as Type 3 or greater based on BARC. Subjects who are attempted to be implanted with the AMPLATZER LAA Occluder, or have been retrospectively enrolled will be included in this analysis.

Reporting:

The following data will be summarized and reported annually to Health Canada.

- Investigator sites and enrollment status
- Demographic and baseline characteristics
- Serious Adverse Events
- Procedural results (procedure success, implanted device size, procedure duration)
- Device closure rates
- Oral anticoagulant use

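### Deaths before consent cannot be seen for retrospective subjects: state whether these subjects enter the primary tests, settle one time origin, and use delayed entry where they are included

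*Protocol*

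**What the plan says.** Protocol 4.2 admits prospective and retrospective subjects. A retrospective subject is enrolled "when consent is obtained after a subject underwent a study device implant attempt that may have been successful or unsuccessful (retrospective" (Protocol 4.5). The same section says "The consent form must be signed and dated by the subject and by the person obtaining the consent, where applicable", and "Prior to enrollment in the clinical study, all subjects will be consented, as required by applicable regulations".

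For Effectiveness 1, Protocol 14.1.1 says "Kaplan-Meier analysis will be used to estimate the event rate of at 24 months (731 days post implant", and "Subjects in this study who receive an implant of the AMPLATZER LAA Occluder will be included in the analysis". For Safety, 14.1.3 says "Subjects who undergo an implant attempt with the AMPLATZER LAA Occluder will be included". Neither population names or excludes retrospective subjects. Section 14.3 does name them for procedure duration, TIA, all-cause death and major bleeding: "Subjects who are attempted to be implanted with the AMPLATZER LAA Occluder, or have been retrospectively enrolled will be included in this analysis".

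Earlier events are collected back to the implant (Protocol 6 and 6.4). For unsuccessful attempts, "AEs that occurred within 7 days following the implant attempt or by discharge, whichever was later, will be captured" (6.3). The only visible limit on how far back enrolment may reach is device approval in the region (Protocol 2).

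Three statements sit badly with this:

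- The synopsis counts the effectiveness endpoints over 24 months from enrollment, while follow-up ends 2 years after implant.
- SAP 1.3 describes a prospective study of subjects yet to be implanted.
- Protocol 14.4 foresees nothing that could compromise interpretation.

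**The concern.** Back-collection of events works only for patients who enrol. Someone who died between the attempt and the consent visit normally never enrols, and so disappears from both numerator and denominator.

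For Effectiveness 1, whose composite includes cardiovascular or unexplained death, this creates immortal time. A retrospective subject is counted at risk from implant, yet could not have had a fatal event before consent. The all-cause death curve has the same problem if its clock also starts at implant, which is inferred.

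Safety works differently. It is a proportion over a fixed early window, so risk time plays no part. The problem is a denominator made up only of survivors.

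Effectiveness 2 is touched only lightly, through fatal ischemic strokes or emboli before consent.

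The goals are fixed and there is no control arm to share the bias. Missed deaths therefore act directly on the comparison that decides success.

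**Working it through.** **The plan's own figure.** The 1000 in Protocol 4.2.2 is a total pooled with other post-approval studies. It cannot be reproduced, because SAP 2.4 is redacted. The stated success rules can be turned into event limits instead.

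**Event limits.** Safety, exact 97.5% bound against 2.66%:
- n=1000 passes at 16 events (bound 2.585%; 17 gives 2.708%), with false success 1.8% when the true rate is 2.66%.
- n=500 passes at 6 events (2.593%; 7 gives 2.863%), with false success 2.0%.

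Effectiveness 1 against 9.6%, n=1000, no censoring, log-log bound: passes at 77 events, false success 2.1%.

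**Effectiveness 1 inputs.** From the plan: 9.6%, 24 months, 97.5% bound. Assumed: share retrospective r, consent lag (uniform), fatal share f of composite events, constant hazards, true rate at the goal.

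**Closed form at the mean lag L.** Cumulative hazard H = −ln(1 − 0.096) = 0.1009. The chance of no fatal composite event by L is S = exp(−f·H·L/24). Non-fatal events before consent are still captured, so the retrospective subjects show 1 − 0.904/S. The study reads (1 − r)·9.6% + r times that rate. Example with r=50%, f=40%, L=6: S = exp(−0.4 × 0.1009 × 6/24) = 0.990; retrospective rate 1 − 0.904/0.990 = 8.68%; study 0.5 × 9.6 + 0.5 × 8.68 = 9.14%.

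**Simulation.** 8000 runs per case, other deaths (10%) censored, retrospective subjects drawn conditional on being alive at consent. False success in %:

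| Retrospective, lag (months), fatal share | Closed-form reading | n=1000 | n=500 | n=300 |
|---|---|---|---|---|
| none | 9.60% | 2.1 | 2.0 | 1.8 |
| 10%, 0–6, 40% | 9.55% | 2.5 | 2.2 | 1.9 |
| 25%, 0–12, 40% | 9.37% | 3.6 | 2.8 | 2.1 |
| 50%, 0–12, 40% | 9.14% | 6.2 | 4.7 | 3.3 |
| 50%, 0–24, 60% (extreme) | 8.21% | 29 | 15 | 9 |

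Monte Carlo error is about 0.2 points near 2–3%. As a check, P(X ≤ 77) at n=1000 for the four closed-form readings is 2.36, 3.65, 6.07 and 30.2%. With delayed entry at consent, every case reads 9.6% with 1.5–2.4% false success.

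**Selective consent (n=1000).** If survivors of a non-fatal pre-consent event are half as likely to enrol, the 25% and 50% cases (0–12 months) give 5.0 and 11%. If they are twice as likely, they give 1.9 and 1.4%, below the 2.1% baseline. The net direction can reverse.

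**Safety.** Let d be the assumed risk of death in the window, with all such deaths before consent. Retrospective rate = (2.66% − d)/(1 − d). For d=0.5%: 2.16/0.995 = 2.17%; at 25% retrospective the study reads 0.75 × 2.66 + 0.25 × 2.17 = 2.54%. False success at n=1000 for d = 0.2, 0.5 and 1.0% is 2.2, 3.1 and 5.1% at 25% retrospective, and 2.8, 5.1 and 12.8% at 50% (baseline 1.8%).

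**Effectiveness 2.** n=1000, 25% retrospective, lag 0–12 months, 10–20% fatal: about 2.5%, against 2.1%.

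**Death curve.** An assumed true 15% reads 14.8, 14.2 and 13.2% in the first three retrospective cases. Delayed entry reads 15.0–15.1% across the cases.

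**Clock.** On the synopsis clock, Effectiveness 1 has no immortal time. But a subject consented 12 months after implant has 24 − 12 = 12 months of planned follow-up (plus the visit window), not 24.

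**The case against.** The strongest objection is that inclusion in the primary tests is not shown. SAP 2.1 and 2.9 and the ends of 14.1.1–14.1.3 are redacted. Other places where a rule could sit are also redacted, empty or not reproduced: Protocol 4.2.2 and 4.2.3, SAP 2.2.3, 2.4 and 2.7, Figure 3 and the Table 2 grid. Section 14.3 names retrospective subjects and 14.1 does not, and SAP 1.3 says prospective. Consent is qualified by local regulations, and the sample consent form was not available, so a waiver cannot be ruled out. All of this stands. It makes the primary-test part conditional. It does not touch the death curve, where inclusion is stated, or the contradictions.

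A reader might infer three stronger things that the documents do not support:

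- That the primary tests are biased toward success overall. Only the missed-death component has a fixed sign; selective consent can offset it.
- That Safety gains immortal time. Its window is fixed, so it cannot.
- That false success is near 29%. That figure needs half the cohort retrospective, lags up to 24 months, 60% fatal events and the pooled n of 1000. The mild case is negligible.

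It can also be said that delayed entry costs power for an unconfirmed condition. That is fair, and the remedy for Effectiveness 1 should depend on confirmed inclusion.

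**Conclusion.** The point holds in conditional form, as something that should be fixed, with moderate confidence. Retrospective subjects enrol only on consent after the attempt, and no visible rule recovers those who died first. If they enter the primary tests, the missed deaths lower the observed Effectiveness 1 and Safety rates against their goals. The net direction, once consent selection is allowed for, is not established.

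The size depends on retrospective share, consent lag and fatal share, none of which is visible. At n=1000 it runs from negligible (2.5% false success) to 3.6–6% in moderate cases, and it is smaller at n=500 or 300. Larger values need extreme assumptions.

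Two parts do not depend on inclusion in the primary tests. The death curve includes retrospective subjects by its own wording. The synopsis clock also contradicts 14.1.1, and planned follow-up cannot deliver it for late-consented subjects.

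**What to change.** 1. Reconcile the synopsis with Protocol 14.1 on one time origin, and SAP 1.3 with Protocol 4.2 and 4.5 on retrospective enrolment. State for each primary test whether retrospective subjects are in it.
2. If they are, and no redacted rule already covers this, analyse Effectiveness 1 from implant with delayed entry at the consent date (Protocol 14.1.1, SAP 2.3.1.2). Protocol 6.1 already records that date. Subjects with a qualifying event before consent do not enter the first-event risk set. Tabulate those events separately, and give the plain from-implant estimate as a sensitivity analysis.
3. Use delayed entry for the all-cause death curve in 14.3 in any case, and for Effectiveness 2 as a sensitivity analysis only.
4. For Safety, report the proportion and exact 97.5% bound by enrolment type and for subjects consented before vascular access. Say plainly that delayed entry cannot repair this window, that the pooled test stays exposed to missed deaths, and that these analyses inform interpretation without changing the decision test.
5. Amend Protocol 14.4 to acknowledge survivor selection.

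Cost: wording, and an entry-time variable in the Kaplan-Meier code. In the mild and two moderate cases, delayed entry loses about 1, 7 and 13% of person-time. Effectiveness 1 power at n=1000, with an assumed true rate of 7.0%, falls from 81% to 79, 78 and 74%; in the extreme case it is 67%. Delayed entry also assumes that consent timing is unrelated to later risk. Safety keeps its population and power.

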5.1 Device Descriptions

The AMPLATZER Cardiac Plug (ACP) (**Figure 1**) and AMPLATZER Amulet Occluder (**Figure 2**) are constructed from a nitinol mesh and consist of a lobe and a disc connected by a central waist. These devices are percutaneous transcatheter devices intended to prevent thrombus

embolization from the left atrial appendage (LAA) in patients who have non-valvular atrial fibrillation. These devices may be considered for use in patients who have a high risk of stroke and bleeding and are deemed by their physician to have an appropriate rationale to seek a non-pharmacologic alternative to long term anticoagulants.

Depending on the device, the lobe ranges in diameter from 16 to 34 mm (**Table 1**) and has stabilizing wires for device placement and retention. The disc is larger in diameter than the lobe, ranging from 20 to 41 mm; both the disc and the lobe contain polyester fabric to facilitate LAAO. There are threaded screw attachments at either end of the device for connection to the delivery and loading cable. Radiopaque markers at either end of the device and at the location of the stabilizing wires allow for predictable placement of the device. The stabilizing wires and polyester patch are secured to the device using polyester thread. A platinum/iridium thread is attached to the nitinol braid.

Accessories packaged with the AMPLATZER LAA Occluder device include the loader, loading cable, loading cable vise, delivery cable, delivery cable vise, and hemostasis valve.

Figure 1: The AMPLATZER Cardiac Plug and key components

Figure 2: AMPLATZER Amulet Occluder key components

Table 1: Model numbers and key dimensions of the AMPLATZER LAA Occluders and delivery system

Reference	ACP Lobe/ Device Size (mm)	Left Atrial Disc Size (mm)	Lobe Length (mm)	Usable Length (cm)	Sheath size
AMPLATZER CARDIAC PLUG					
9-ACP-007-016	16	20	6.5	80	9F
9-ACP-007-018	18	22	6.5	80	10F
9-ACP-007-020	20	24	6.5	80	10F
9-ACP-007-022	22	26	6.5	80	10F
9-ACP-007-024	24	30	6.5	80	13F
9-ACP-007-026	26	32	6.5	80	13F
9-ACP-007-028	28	34	6.5	80	13F
9-ACP-007-030	30	36	6.5	80	13F
AMPLATZER Amulet Occluder					
9-ACP2-007-016	16	22	7.5	80	12F
9-ACP2-007-018	18	24	7.5	80	12F

Reference	ACP Lobe/ Device Size (mm)	Left Atrial Disc Size (mm)	Lobe Length (mm)	Usable Length (cm)	Sheath size
9-ACP2-007-020	20	26	7.5	80	12F
9-ACP2-007-022	22	28	7.5	80	14F
9-ACP2-007-025	25	32	10	80	14F
9-ACP2-007-028	28	35	10	80	14F
9-ACP2-007-031	31	38	10	80	14F
9-ACP2-007-034	34	41	10	80	14F

Future generation AMPLATZER™ LAA Occluders may be used in the study upon approval by Health Canada.

5.2 Device Accountability

The AMPLATZER LAA Occluder devices are market released in the countries where this study will be conducted. Therefore, there are no tracking requirements for this study. Information regarding opened, introduced, and implanted devices will be recorded on the Procedure and Product Out of Service (where applicable) eCRFs.

6. Study Procedures

This study will be conducted in accordance with the clinical protocol and IFU. All persons participating in the conduct of the study will be qualified by education, training, or experience to perform study-related tasks.

The study will not commence at each selected site until Abbott receives written approval from the IRB/EC and relevant regulatory authorities, and all required documents have been collected from the participating sites.

Figure 3 below describes the study flowchart for subject screening, consent, enrollment and follow-up through the 2-year follow-up visit. **Table 2** outlines the testing and assessments required per study visit interval for subjects who are implanted with an AMPLATZER LAA Occluder.

Figure 3: Study flowchart for subject screening, consent, enrollment and follow-up

[figure not shown]
[figure not shown]
[figure not shown]

Table 2: Study visits and assessments (subjects who are implanted with an AMPLATZER LAA Occluder)

Follow up visit timing begins from the date of the procedure for both prospective and retrospective enrollments.

The electronic Case Report Forms (eCRFs) to be completed for enrolled subjects per the study visit intervals are:

- Baseline – Baseline, Enrollment, Modified Rankin Scale, Medication, and Echo
- Procedure – Procedure, Echo, Medication
- Discharge, 2M, 6M, 12M and 24M – Follow-up, Echo (as required), Medication
- Unscheduled visit - Follow-up, Medication, Echo (as required)

For retrospective enrollments, the applicable Baseline, echo, and adverse events CRFs should be retrospectively completed based on information from the subject's medical records. Retrospective data should include any adverse events from the date of implant or attempted implant. Protocol required follow up visits will begin after the subject's trial enrollment date.

Additional eCRFs, reports and assessment noted below should be completed upon occurrence, and/or as applicable:

- Withdrawal eCRF
- Adverse Event eCRF
- Protocol Deviation eCRF
- Death eCRF
- Stroke/TIA Assessment eCRF
- Echo eCRF
- Modified Rankin Scale (**Appendix G**: Modified Rankin Scale (mRS) (complete 90 days after confirmed stroke)

Suspected stroke or TIA

- **Prospective enrollment**: If a stroke or TIA is suspected, the subject should be seen by a neurologist or neurosurgeon for evaluation and appropriate neurological testing (CTA (computed tomography angiography) or MRA (magnetic resonance angiography)). If a stroke is confirmed, a TOE is required as soon as possible, but no later than 7 days to confirm device placement, LAA flow parameters and presence/absence of device-related thrombus. See **Section 8.1** for further details.
- **Retrospective enrollment**: If a previous stroke or TIA was suspected, any neurologic evaluation data including neurological testing and echo imaging should be submitted through the Stroke/TIA Assessment eCRF and any previous AEs due to the suspected stroke or TIA should be submitted according to **Section 8.1**.

6.1 Screening/Enrollment/Baseline

The following baseline and enrollment activities are performed as part of the screening process:

- Informed consent process
- History and physical
- Cardiovascular and medical exam
- Pregnancy testing for women of childbearing age
- TOE (optional if a TOE is performed on the day of procedure)
- Modified Rankin Scale
- Medication assessment
- CHA₂DS₂-VASc score:

Table 3: CHA₂DS₂-VASc score

CHA₂DS₂-VASc	Score
Congestive heart failure/LV dysfunction	1
Hypertension	1
Age > 75	2
Diabetes mellitus	1
Stroke/TIA/TE	2
Vascular disease [prior myocardial infarction, peripheral artery disease or aortic plaque]	1
Age 65-74	1
Sex category [i.e. female gender]	1

- HAS-BLED score:

Table 4: HAS-BLED score

HAS-BLED	Score
Hypertension history (uncontrolled, > 160 mmHg systolic)	1
Abnormal renal function/renal disease (dialysis transplant, creatinine > 2.6 mg/dL or > 200µmol/L)	1
Liver disease (cirrhosis, bilirubin > 2x normal AST/ALT/AP > 3x normal)	1
Stroke history	1
Bleeding, anemia, or predisposition to bleeding	1
Labile INR (Unstable/high INR's, or poor time (< 60% time in therapeutic range))	1
Elderly - Age ≥ 65 years	1
Drugs - Medication usage predisposing to bleeding (antiplatelet agents, NSAIDs)	1
Alcohol usage history (> 8 drinks/week)	1

The principal investigator or delegated study personnel is responsible for screening potential subjects to determine subject eligibility for the study. Enrollment information (date of consent, enrollment criteria, etc.) will be recorded in the subject's hospital records and on the Baseline eCRF. For prospective subjects, the Baseline eCRF should be submitted within one week of signing the informed consent form. Baseline eCRFs for retrospectively enrolled subjects will capture data before attempted implant, collected from their medical history.

For prospective subjects, if a subject does not meet criteria for AMPLATZER LAA Occluder implant, the subject cannot participate in the study. The Baseline eCRF (consented screen failure), as applicable, must be completed and the subject should be withdrawn. If the subject was enrolled (i.e. consented and vascular access initiated), but does not get a device implanted due to anatomy or other reason, the Baseline, Procedure, and Withdrawal eCRFs should be completed.

Serious adverse events will be reported from the time vascular access was initiated to the time the subject concludes the study. Adverse Event eCRFs should be completed, as applicable.

